Study protocol

„Effect of The mother's active pushing
at cesarean delivery “

The target and the reasons for the study

Caesarean section (C-section) is one of the most commonly performed operations for women all over the world. Currently around every 3rd baby (31.3% on average) born in German hospitals is delivered by C-section⁽¹⁾⁽²⁾. Women who deliver by C-section have been reported to express less satisfaction with their birth experience than women delivering vaginally ⁽³⁾. Some women also express strong feelings of loss, failure, and anger during C-section⁽⁴⁾. These feelings are likely related to stress, pain, and fatigue associated with major surgery and the psychological status of the patient and a stressor or trigger in the development of postnatal depression ⁽⁴⁾. Also, some studies suggested that the mother-infant bonding is affected by the mode of the delivery being worse with C-section.

In this study, we will evaluate how the participation of patients in the delivery process during the C-section by pushing will affect the patients' experience. This is done in anticipation that this participation will alleviate the severity of the intraoperative discomfort, the postoperative pain, and improve the breastfeeding and patient's satisfaction by granting the patient a higher feeling of control.

There are different techniques for performing C-Section of which some Techniques are performed with the participation of the mother and others without. Currently, there is no consensus on a standardised technique with convincing evidence of its superiority. The first approach of this modification of the C-section was described in 2008 by Smith et al. and was termed the "natural caesarean" ⁽⁵⁾.

In 2016, a prospective randomised controlled trial was conducted at the Charity Berlin Hospital, aiming to evaluate the safety of patient's delivery experience of the modified C-section (participation of the mother during C-section) and early skin-to-skin contact(STS). Parameters of perinatal outcome for both mother and infant were assessed using modified Likert-Scales and a standardized questionnaire. Primary outcome measures were birth experience and satisfaction for both parents. Parameters of breastfeeding, consecutive problems, APGAR Scores, blood loss and perioperative complications were secondary outcome measures. The trial concluded that birth experiences and

breastfeeding was rated significantly higher in the modified C-section group with the active participation of the mother compared to a classical C-section ($p < 0.05$). However, there were no significant differences regarding the neonatal outcome, intraoperative and postoperative complications. Major critics against

this study are that the authors did not analyse one factor but a combination of several factors which hinders clear evaluation. In addition, by creating a whole construct called “the charity birth”, several scientists criticize that this will promote C-section in cases where vaginal birth would be the suggested option.⁽⁶⁾

Therefore, we decided to only evaluate the effects of one technique during C-section. This does not promote C-section, however, might improve outcomes for patients who have to undergo C-section and alleviate postoperative negative effects caused by this procedure.

Characterisation of the subjects

Patients, who are getting a scheduled C-Section and having no contraindication for valsalva manoeuvres are eligible for this study. The gestational week should be between 37 and 42 weeks. Patients have to provide informed consent to this study. Patients must have epidural anaesthesia. They must understand the German language in order to understand information during C-section and correctly fill-out the questionnaires. Emergent C-sections or pregnant women known with chronic pain, severe preeclampsia or HELLP-Syndrome will be excluded

Inclusion criteria

- Minimum age of 18 years
- Written consent
- Pregnant women between 37 – 42 weeks
- No fetal abnormalities.
- Scheduled primary C-Section (category 3&4 NICE guidelines) with epidural anaesthesia

Excluding criteria

- Emergent C-section
- Contraindication for epidural anaesthesia.
- Multiple pregnancies
- Scheduled C-section with placenta previa, accreta, increta or percreta.
- Secondary C-section
- Contraindication for Valsalva manoeuvre

- Known psychiatric illnesses
- Known chronic Pain, taking Pain killers regularly

Studientyp

Prospective randomized single-centre study

Measurements, findings and observations

During the C-section, the patient will be guided to push after the uterotomy, aiming to participate in the process of delivery during the surgery. Patients will fill out a survey designed to assess pain severity and satisfaction level.

1. Intraoperative and Postoperative pain at different time points (day 0,1,2 postoperatively) depending on validated numerical pain Scale (7).
2. Psychological status and the satisfaction of the patient postoperatively using the validated Edinburgh Postnatal Depression Scale (EPDS)(8).
3. Neonatal outcome according to APGAR score and pH Level from the umbilical cord.
4. the breastfeeding depending on Breastfeeding Self-Efficacy Scale, Short Form (BSES-SF) (9)(10).
5. The duration of the surgery and its complications (intraoperative haemorrhage, wound complication, postpartum haemorrhage (PPH) and surgical injury).
6. A surgeon questionnaire evaluating the actual performance of the procedure.

A detailed description of the course of study

Antenatally, pregnant women will be evaluated for their eligibility for this study. Patients planned for primary C-section will be informed on preoperative visits. (category 3&4 NICE guidelines). If so, written informed consent will be collected from the patients prior to their participation in this study. Patients will be informed about the postoperative assessment in order to evaluate the effects of C-section techniques. As described in the patient information, there will be general information about the procedure and that communication and maternal participation will be evaluated. An explanation of pushing or not-pushing, which both represent standard-techniques, will not be provided in

detail, to avoid expectation bias. Patients will be randomized by the study assistant using a 1:1 strategy. Patients will be assigned an identifier number upon their enrolment to the study. The allocation of participants, to either the control or the test group, will be randomly allocated using R software. This is to eliminate any human interference or bias in patients allocation.

All participating surgeons will attend specialized training during which the study principles and the variations in C-section technique will be explained. Directly before surgery, surgeons will be informed about the randomization results.

Control group: non-pushing

This method describes the standard technique routinely performed by about 70% of all C-sections. After uterotomy the child will be delivered by the doctor without special information given to the patient. Patients will be informed about the feeling of abdominal pressure. The assistant will perform abdominal pressure to help deliver the baby. The umbilical cord will be clamped and the baby will be handed over to the midwife. The midwife will try to enable early skin-to-skin contact and perform routine care for mother and child.

Intervention group: pushing

This method describes the standard technique routinely performed by about 30% of all C-sections. After uterotomy the patient is informed that the child will be delivered soon. The surgeon explains and encourages the mother to push when she is asked to deliver the baby. The assistant will help the mother with abdominal pressure. During delivery, which routinely happens with three pushes, the surgeon informs the mother about the progress (head, shoulders, belly). After delivery, the surgeon directly shows the baby to the mother and praises the mother for her efforts. The umbilical cord will be clamped and the early skin-to-skin contact will be enabled if medically accepted.

[figure not shown]
Methods

Since there is currently no standardized questionnaire for the assessment of the patient's well-being after the C-section, that's why we created the questionnaire in accordance of previous studies consisting of the following:

- validated numerical pain Scale for assessment of the intraoperative and postoperative pain.

- validated Edinburgh Postnatal Depression Scale (EPDS) for assessment of the Psychological status and the satisfaction of the patient postoperatively.
- Self-Efficacy Scale, Short Form (BSES-SF) for assessment of the breastfeeding at day 1-2 postoperative. Since the (BSES-SF) not validated in the German language, we will translate the questionnaire in Germany and validate it as a part of this study.
- We added extra questions on the questionnaire using a Likert scale for assessment of the patient's feelings during and after the surgery.

After surgery objective assessments will be documented including postoperative complications, blood loss, fetal outcome. The surgeon will fill out a survey investigating the surgeons' impression. Directly after child delivery patients will be first asked about the pain sensation during the delivery according to a VAS scale. Postoperatively at 4-6 hours after the surgery, patients will fill out the first survey. At day 1 and day 2 postoperatively, patients will fill out the following surveys. Data, which is collected from the surveys, will be encoded pseudo-anonymous. Recording of the complications will be performed in the first 3 days after delivery, as the usual hospital stay ranges between 3-5 days. This period covers all usual postoperative complications. Recording postpartum pain medications is essential as we cannot predict who will require which level of pain relievers (mild analgesics without opioids, weak opioids and strong opioids).

The aim of this study is to evaluate if the mother's active pushing during the C-section reduces pain during child delivery

Primary endpoints

- The severity of the intraoperative pain

Secondary endpoints:

- The severity of the postoperative pain
- Patient's satisfaction with the operation and her participation
- Patient's psychological status postoperatively
- Breastfeeding after early Skin to Skin contact (SSC)
- Neonatal Outcome
- Duration of the hospital stay, duration of the surgery and its complications (intraoperative Haemorrhage, wound complication, PPH and surgical injury)
- Surgeon's satisfaction with the procedure

The data collection and documentation

Data will be collected after taking the patient's written informed consent. Patients will be given pseudonyms. Only the study leader will have access to the files.

Data privacy:

Before a patient is enrolled in the study, written informed consent will be collected with the patient's verbal acceptance and signature to join the study. No personal or identifiable data will be published or passed on to third parties. The approval of the participants can be cancelled at any time. This cancellation will not influence further medical care. In the event of a dropout, the patient's data will be deleted and will not be included in the analysis. The data will only be used for scientific purposes. The results will be published in research reports, posters and scientific publications in accordance with the Data protection and privacy policy. The collected data will be archived for 10 years.

Unwanted events

There are no expected specific complications regarding this technique since both techniques are routinely used. However, potential surgical complications associated with cesarean section are:

- Maternal complication (Endometritis, wound complication, haemorrhage, infection, surgical injury of the urinary bladder, the small intestine and rarely the ureter), thromboembolism, ileus, septic pelvic thrombophlebitis and rarely hysterectomy
- Fetal and neonatal risks (iatrogenic prematurity, iatrogenic birth trauma, transient tachypnoea of the newborn and neonatal adaption syndrome)
- Anaesthetic complications.
- Complications regarding the Valsalva manoeuvre are only described for prolonged pushing during vaginal delivery. These complications are very unlikely during C-section. (11)

Only patients with indicated C-section will be included. Thereby, patients will not be exposed to additional risk as described above compared to vaginal delivery.

Evaluation /Biometrics

Descriptive statistics will be used to assess patients characteristics. Student T-test or Mann Whitney U test will be used to for continuous data to compare parametric or nonparametric data sets, respectively and the chi-square test will be applied for categorical data.

The primary evaluation should be based on the intention-to-treat population, i.e. all patients who were randomized will be included in the evaluation. With regard to the primary end point, a very timely recording will take place, so that only a negligible number of missing values can be assumed.

In case of doubt or missing values, it will be replaced by the maximum observed VAS values in the study, which is a relatively simple elimination procedure and is easy to implement. As sensitivity analyses other imputation methods will be performed.

We will conduct ANCOVA analyses to see how postoperative pain medication influences the study outcome. The WHO pain medication scale will be used to group the patients.

Power calculations

Biometric Analysis was performed with the kind assistance of [name], Institut für Biometrie ,MHH. Please see the attached document.

There is a study from Berlin (6) on the subject, but this analysed a self-created composite variable on satisfaction and did not evaluate the sensation of pain separately. There are no known studies which assessed the intraoperative pain during child delivery. The best approximation remains the direct postoperative pain. An older study (12) was a randomized four-therapy-arm study (placebo, diclofenac, propacetamol or diclofenac and paracetamol directly after delivery) which assessed postoperative pain after caesarean section at several time points. This study reflects the routine pain medication used in our clinics and was therefore selected.

In the study analysing postoperative pain after caesarean section the mean VAS scores at 6 hours ranged between 3.4 and 3.9 with a standard deviation of 1.7-2.0. Since we want to evaluate intraoperative pain, we expect higher mean VAS scores between 6-7. We will calculate with a standard deviation of 2.0. Based on the findings of Armbrust et al and our clinical experience we expect a therapeutic effect of 15-20% which results in a mean VAS reduction of 0.8. Applying a two-sided T-Test for independent samples at a significance level of 0.05, a mean difference of 0.8 between the groups and a standard deviation of 2, we will need 100 patients per treatment arm to detect a difference between both treatment groups with a power of 80%.

There is currently no prognostic factor that is known in advance to influence outcome in a certain direction. Thus, stratification is not planned.

+

References:

1. Wacker J. Geburtshilfe. Kaiserschnitt vs. Natürliche Geburt. Geburtshilfe Frauenheilkd. 2010;70(10):840–3.
2. Beckmann M W, Bader W Bl. Finanzierung und finanzielle Probleme von Leistungen und Strukturen im Fachgebiet Gynäkologie und Geburtshilfe im Jahr 2011 – allgemeine Aspekte und geburtshilfliche Versorgung. Geburtsh Frauenheilk. 2011.

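### The aim credits active pushing alone, but the pushing arm also scripts communication that the control arm lacks; the aim and conclusion should name both

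*Combined protocol and SAP*

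**What the plan says.** All references are to the combined protocol and SAP.

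- **The single-factor intent.** In the opening section on the target and reasons for the study, the main criticism of the earlier randomised trial is that "the authors did not analyse one factor but a combination of several factors which hinders clear evaluation". The plan's reply is "Therefore, we decided to only evaluate the effects of one technique during C-section".
- **The stated cause.** The title names the mother's active pushing. So does the aim, given at the end of Methods just before the primary endpoint: whether active pushing reduces pain while the child is delivered.
- **Control arm** (Control group: non-pushing). "After uterotomy the child will be delivered by the doctor without special information given to the patient". One message is given: "Patients will be informed about the feeling of abdominal pressure". After the cord is clamped, the baby goes to the midwife.
- **Pushing arm** (Intervention group: pushing). "After uterotomy the patient is informed that the child will be delivered soon". The surgeon then explains and encourages the push, tells the mother during delivery which part of the baby has emerged, shows her the baby directly afterwards and praises her.
- **What patients are told.** The detailed description of the course of study says the patient information will mention that communication and maternal participation are both being evaluated.
- **Primary rating.** Methods has the mother asked, immediately after the birth, how painful the delivery was.

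**The concern.** The plan sets itself a standard, one factor and not a combination, and its title and aim are worded as though that standard were met. It is met in part: the earlier trial is described as combining maternal participation with early skin-to-skin contact, and here skin-to-skin contact is planned in both arms. The scripted communication, however, still differs between the arms along with the pushing.

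This communication could plausibly affect the outcome. The plan lists less intraoperative discomfort among the hoped-for benefits of participation, and ends that sentence with better "satisfaction by granting the patient a higher feeling of control". Being told what is happening could also give a mother that feeling, whether or not she pushes.

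At stake is what may be concluded. If the pushing arm reports less pain, a conclusion worded like the aim would say that pushing did it. A unit acting on that conclusion could ask mothers to push and drop the commentary, and the trial would hold no evidence for doing so.

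**Working it through.** **Step 1. The two arm descriptions side by side.**

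| Element | Pushing arm | Control arm | Separable from pushing? | Timing against the pain rating |
|---|---|---|---|---|
| Announcement that delivery is near | Scripted | Not scripted | Arguably; it can also be read as leading into the explanation of the push | Before |
| Explaining and encouraging the push | Scripted | None | No | Before |
| Progress commentary | Scripted | Not scripted | Most clearly; it could be given to a mother who is not pushing | Before |
| Message about abdominal pressure | Not mentioned | Scripted | Not applicable | Not stated |
| Showing the baby directly | Scripted | Text is silent | Yes | Order not stated |
| Praise for the effort | Scripted | Text is silent | Treated here as part of pushing | Order not stated |
| Early skin-to-skin contact | Planned, if medically acceptable | Planned: "The midwife will try to enable early skin-to-skin contact and perform routine care for mother and child" | Not applicable; planned in both arms | Not stated |

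The missing communication in the control arm is not inferred from silence: that arm is defined as delivery with no special information. Silence is all there is for showing the baby.

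Two elements therefore differ by script, precede the primary rating and are at least arguably separable from pushing: the commentary and the announcement.

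**Step 2. What the comparison estimates.** Write P for the effect of pushing itself and C for the added effect of the communication, including any interaction. The difference between the arm means estimates

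Δ = P + C.

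That is one equation in two unknowns. The plan has no third arm, no matched communication for controls and no analysis meant to separate the two. To illustrate, take the planned Δ of 0.8 VAS points and let communication account for a share s, so that P = 0.8 × (1 − s). The values of s are assumptions; the documents give none.

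| Assumed s | P | C | Δ |
|---|---|---|---|
| 0 | 0.8 | 0 | 0.8 |
| 0.25 | 0.6 | 0.2 | 0.8 |
| 0.50 | 0.4 | 0.4 | 0.8 |
| 0.75 | 0.2 | 0.6 | 0.8 |

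Every row predicts the same arm difference, so the data could not tell the rows apart.

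**Step 3. Is the sample size affected?** Inputs from Power calculations: two-sided t-test, α = 0.05, difference 0.8, SD 2, power 80%, 100 per arm.

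- Standardised difference: 0.8 / 2 = 0.4.
- Normal approximation: n = 2 × (1.960 + 0.842)² / 0.4² ≈ 98.1, so 99 per arm; power at 100 per arm is 80.7%.
- Exact t-test: n = 99.08, so 100 per arm; power at 100 per arm is 80.4%.

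The plan's 100 per arm and 80% are reproduced. They refer to Δ, the difference between the arms as delivered, and do not change when Δ is given a more accurate name.

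**The case against.** The strongest reply is that the plan never meant silent pushing. It speaks of one technique, not one ingredient; it describes each arm as a routine technique (about 70% and 30% of C-sections); and under Measurements it says the patient is guided to push. On this reading, active pushing is a short name for a procedure that the arm description sets out in full. The commentary appears in the same sentence as the pushes, and under epidural anaesthesia feedback on each push may be part of guiding it. The patient information, moreover, already names communication.

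Much of this stands. The trial is a legitimate pragmatic comparison of two routine practices, the line between pushing and its communication is a matter of judgement, and the plan's treatment of communication is inconsistent, not silent. That keeps the point minor. It does not remove it: a comparison of whole techniques supports a conclusion about whole techniques, and neither the title nor the aim says that pushing is shorthand for one. The objection therefore supports the rewording.

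A reader might go further in four ways that the documents do not support:

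- *The comparison is biased or invalid.* The communication is part of the assigned procedure, so randomisation supports a valid comparison of the two procedures as described.
- *The trial is underpowered for pushing.* The sample size was set for the arm difference, and no share for communication is known.
- *Controls receive no communication, or never see the baby.* They receive the abdominal-pressure message, and their script does not rule out showing the baby.
- *Showing the baby distorts the primary pain rating, or bears only on secondary endpoints.* Neither can be said, because the order of showing and rating is not stated.

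**Conclusion.** The point holds as a minor one about attribution. The trial can show whether guided pushing with its accompanying communication changes reported pain compared with routine non-pushing delivery. It cannot show that pushing alone does so, which is what the title and aim say. Type I error, power and the planned analysis are untouched.

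The conclusion assumes that surgeons follow the two scripts as written, and that at least the progress commentary could be given without pushing. If control surgeons in practice comment just as much, the gap narrows. How much of any effect communication might supply is unknown and is not assumed here.

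**What to change.** Change wording only:

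1. **Aim (end of Methods).** For example: *to evaluate whether guided pushing with its accompanying communication lowers pain during delivery compared with routine non-pushing delivery*. This brings the aim into line with what patients are told.
2. **Conclusion.** Use the same label when reporting the primary and secondary endpoints.
3. **Single-technique sentence (opening section).** Amend it, without deleting it, to say that the trial evaluates one routine technique, guided pushing including its communication, with early skin-to-skin contact planned in both arms.
4. **Satisfaction and other secondary endpoints.** Note that showing the baby is scripted only in the pushing arm, that the control text is silent on it, and that its order relative to the pain rating is not stated. Leave it out of the aim, which concerns pain during delivery.

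Procedures, patient numbers and analysis stay as they are. The cost is that the conclusion concerns a package and not pushing alone, which is all that the two arms can support.

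### The EPDS endpoint has no stated assessment day and no preoperative score, so it can describe only early postoperative mood, and less precisely than it could

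*Combined protocol and SAP*

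**What the plan says.** The protocol names the EPDS twice, each time without a day. Under Measurements, findings and observations, item 2 is "Psychological status and the satisfaction of the patient postoperatively using the validated Edinburgh Postnatal Depression Scale (EPDS)(8"). Under Methods, the questionnaire includes the "validated Edinburgh Postnatal Depression Scale (EPDS) for assessment of the Psychological status and the satisfaction of the patient postoperatively". The breastfeeding scale in the same Methods list does have a time: "for assessment of the breastfeeding at day 1-2 postoperative".

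The schedule of patient questionnaires comes later under Methods: "Postoperatively at 4-6 hours after the surgery, patients will fill out the first survey", and then "At day 1 and day 2 postoperatively, patients will fill out the following surveys". No later patient-reported contact is described. Complications are recorded for three days.

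Before surgery, the course-of-study section describes eligibility, information and consent at preoperative visits, but no questionnaire. Under Evaluation/Biometrics, continuous outcomes are compared by t-test or Mann-Whitney test. The only ANCOVA planned concerns postoperative pain medication.

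The opening rationale describes feelings around a caesarean as "a stressor or trigger in the development of postnatal depression". The exclusion criteria include "Known psychiatric illnesses".

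**The concern.** A secondary endpoint needs a defined measurement time. Three patient questionnaires are planned, and the text does not say which of them carries the EPDS or which score enters the comparison. That leaves a choice to be made after the data are seen.

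The schedule also limits what the score can mean. The rationale treats the caesarean experience as a possible trigger for a condition that develops afterwards, while patient reporting stops two days after the trigger. With a depression scale as the measure and no stated limit on interpretation, a null result could be reported as no effect on postnatal depression, and a favourable one as protection. A day-2 score supports neither statement.

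Finally, women differ in mood before they reach the operating theatre. Without a preoperative score, that variation is part of the noise against which the arms are compared, and a chance imbalance can be neither seen nor adjusted for.

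**Working it through.** **The plan's own figure.** Under Power calculations: two-sided 5% level, 80% power, difference 0.8, SD 2, so the standardised difference is 0.8/2 = 0.40. The normal approximation gives n = 2 × (1.960 + 0.842)² / 0.40² ≈ 98.1, rounded up to 99 per arm. The exact t-test gives 99.08, rounded up to 100. With 100 per arm the exact power is 0.804. The stated 100 per arm reproduces. It concerns the primary pain endpoint; no calculation is given for the EPDS.

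**What 100 per arm can detect on the EPDS, unadjusted.** Detectable standardised difference at 80% power ≈ (1.960 + 0.842) × √(2/100) = 0.396. The exact t-test gives 0.398, about 0.40.

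**Gain from a preoperative score.** With correlation r between the preoperative and day-2 scores, ANCOVA multiplies the residual variance by 1 − r², and so the detectable difference by √(1 − r²). The documents give no r; 0.4 to 0.7 is an assumption.

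- r = 0.4: variance removed 0.16; detectable difference 0.398 × √0.84 = 0.365; an unadjusted test would need 100/0.84 ≈ 119 per arm for the same precision.
- r = 0.7: variance removed 0.49; detectable difference 0.398 × √0.51 = 0.284; an unadjusted test would need 100/0.51 ≈ 196 per arm.

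These figures refer to the t-test setting. They do not transfer exactly to the Mann-Whitney test.

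**How much of the score could refer to the time before surgery.** The documents give no recall period. For an assumed window of W days and completion d days after surgery, the preoperative share of the window is (W − d)/W, with a floor of 0. The 4-6 hour survey is taken as d = 0.25.

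| Assumed W (days) | 4-6 hours | Day 1 | Day 2 |
|---|---|---|---|
| 1 | 75% | 0% | 0% |
| 2 | 88% | 50% | 0% |
| 3 | 92% | 67% | 33% |
| 7 | 96% | 86% | 71% |
| 14 | 98% | 93% | 86% |

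On day 2 the share exceeds one half only if (W − 2)/W > 0.5, that is, if W > 4. The table counts calendar days equally. A woman may give the day of surgery more weight, so these are shares of the window and not of the score. The table also shows why the assessment day has to be fixed: for any one window longer than a day, the three surveys cover different mixtures of time before and after surgery.

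**The case against.** The strongest reply is that the plan never sets out to answer a question about postnatal depression. The condition appears once, as background. The stated aim is pain during delivery. The anticipated benefits are intraoperative discomfort, postoperative pain, breastfeeding and satisfaction through a greater feeling of control. The endpoint itself is worded as psychological state after surgery. This stands. A reader might infer that the trial was motivated by a depression question it cannot answer, but the documents do not support that.

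Three other strong readings also fail.

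- **That the score mainly reflects mood before the operation.** This depends on a recall window that the documents do not state. On day 2 the share runs from 0% to 86% over the windows shown.
- **That the missing baseline biases the result.** Allocation is randomised 1:1, and chance imbalance is already covered by the type I error of the planned test. The loss is precision.
- **That excluding known psychiatric illness is a further defect.** It may remove some high scorers, but it would also tend to narrow the variation in prior mood.

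It is also fair to say that placing the EPDS at 4-6 hours to day 2 is an inference from the survey schedule, and that neither a figure printed just before Methods nor the questionnaire itself was available in the text reviewed. If either states a day for the EPDS, that part of the point falls away. The limit on interpretation and the precision argument remain unless a later or preoperative EPDS is shown there.

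A last objection is that this is a secondary endpoint without its own power calculation, so a precision gain is optional. That is correct as to urgency. It is not a reason to forgo a gain that costs so little.

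**Conclusion.** The point holds in a limited form. In the text, the EPDS has no stated assessment day, the last patient survey is on day 2, and no preoperative score is planned. The endpoint can therefore describe early postoperative mood. It cannot support a conclusion about depression arising later, whatever the time of onset, because nothing after day 2 is observed.

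The comparison between arms is unbiased as planned, but less precise than it could be. If r lies between 0.4 and 0.7, a preoperative covariate lowers the detectable standardised difference from about 0.40 to 0.36-0.28 at 100 per arm. That range depends on the assumed correlation. The limit on interpretation depends only on the schedule. The primary endpoint, the sample size and the treatment are not affected.

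**What to change.** 1. Give the same EPDS form once at the preoperative visit, after consent and before randomisation.
2. State day 2 as the EPDS assessment day for the endpoint.
3. Compare arms on the day-2 score by ANCOVA with the preoperative score as covariate, and state in advance how a missing preoperative score is handled.
4. State that the endpoint is early postoperative mood and that no conclusion on postnatal depression will be drawn from it.

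The cost is one short extra form per woman at an existing visit, one covariate, a few missing baseline scores and some wording.

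A later EPDS by post or online is optional. It is needed only if the sponsor wants to conclude on postnatal depression. It is not free: follow-up as described ends at three days and data are held under pseudonyms, so contact after discharge would need consent wording and contact arrangements, and some non-response should be expected.
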